1.2. Summarized Details of Investigational Products

The below description is taken from the *QuikClot 510(k)* Summary, dated April 11, 2013.

1.2.1. Device Description

The QuikClot® Radial® pad is made of a soft, white, kaolin-impregnated gauze. The QuikClot® Radial® pad will be provided in a kit form that consists of a hemostatic pad and an adhesive bandage (Figure 1). The adhesive bandage is a Direct Pressure (DP) Bandage. The hemostatic pad is a hemostatic dressing made of soft, white, kaolin impregnated gauze, configured in a 0.8" diameter by 1.5" long roll. The QuikClot® Radial® pad utilizes a layered clay hemostat, kaolin USP, which is bound to medical gauze. The QuikClot® Radial® pad are provided in a sterile, intuitive, simple to use dressing format that conforms readily to the wound. The DP Dressing is a Class 1 exempt device and serves as a fixation/compression bandage which is in contact with the hemostatic dressing, but is not in direct contact with the wound. In the present trial either a Coban™ bandage or a Tegaderm™ dressing will serve as a fixation/compression bandage instead of the supplied DP dressing to secure the QuikClot® Radial® pad over the arteriotomy site.

1.2.2. Intended Use

The *QuikClot® Radial®* pad is applied topically as an adjunct to manual compression and is indicated for the local management and control of surface bleeding from vascular access sites, percutaneous catheters or tubes utilizing introducer sheaths up to 12 Fr and up to 7 Fr and for patients on drug/induced anti-coagulation treatment.

1.2.3. Technological Characteristics and Substantial Equivalence

1.2.3.1. *QuikClot® Radial®* Pad

The *QuikClot® Radial®* pad is intended for control of surface bleeding from vascular access sites, percutaneous catheters or tubes utilizing introducer sheaths up to 12 Fr. There are several marketed devices with similar indications that utilize alternate technologies to achieve the same indications as the proposed device, such as the Vascular Solutions D-Stat Dry, WoundStat, and the ChitoFlex™ Surgical device. The *QuikClot® Radial®* pad is identical in technology to the *QuikClot® Interventional™* hemostatic bandage.

The *QuikClot® Radial®* pad and the predicate devices are similar in that they are all indicated as an adjunct to manual compression and are indicated for the control of surface bleeding from vascular access sites and percutaneous catheters or tubes and reducing the time-to-hemostasis in patients undergoing diagnostic endovascular procedures utilizing introducer sheaths.

1.2.3.2. 3M™ Coban™ Self-Adherent Latex-free Wrap

Figure 2. Coban™ self-adherent latex-free wrap

3M™ Coban™ Self-Adherent Latex-free Wrap is a sterile, cohesive elastic wrap constructed from a nonwoven material and elastic fibers (Figure 2). The cohesive properties allow the wrap to stick to itself but not to other materials or skin. It is supplied in individually packaged sterile rolls. This product is not regulated under the FDA, and a MSDS is not required for this product by the OSHA Hazard Communication Standard (29 CFR 1910.1200) because, when used as recommended or under ordinary conditions, it should not present a health and safety hazard. Coban™ self -adherent wrap is intended for use as an elastic wrap to provide compression or support, or to secure dressings or devices. 3M Coban™ Sterile Self-Adherent Wrap

(Catalog No: 1582S, 2" X 5 yd) or a generic equivalent (CardinalHealth, Catalog No: CAH25LFS) will be used in this study.

1.2.3.3. 3M™ Tegaderm™ Transparent Film Dressing

Tegaderm™ is a transparent medical dressing manufactured by 3M™. Tegaderm™ Film consists of a thin film backing with a non-latex, hypoallergenic adhesive (Figure 3). The dressing is breathable, allowing good oxygen and moisture vapor exchange. It is waterproof and impermeable to liquids, bacteria, and viruses. An intact dressing protects the site from outside contamination. Tegaderm™ transparent dressings can be used to cover and protect wounds and catheter sites. Tegaderm™ transparent film dressings are routinely used in the Cardiac Cath Labs of MRH.

Figure 3. Tegaderm™ film dressing

1.3. Device Usage

Application of the *QuikClot® Radial®* pad will be performed by properly trained interventional cardiologists.

Application of the TR Band® will be performed by properly trained interventional cardiologists or cath lab technicians. Proper training for physicians for either device is defined as performing 2 run in procedures prior to enrolling patients in this study, supervised by a cardiologist or industry representative experienced with the either device. For cath lab technicians, proper training will be meeting the qualifications outlined by the Memorial Cardiac and Vascular Institute cath lab protocol for application of the TR Band®. [name], [name] and [name] are properly trained with the use of the *QuikClot® Radial®* pad hemostatic device and TR Band®.

1.3.1. The method for using the *QuikClot® Radial®* pad with a Coban™ Self-Adherent Wrap is as follows:

After an end-procedure ACT is drawn and the blood pressure is recorded, the arterial access sheath will be partially pulled out of the radial artery, exposing approximately 4 cm of sheath. The level of the access site will be marked on the medial and/or lateral side of the palmar surface of the wrist with a sterile marker pen so that once the pad is applied and covering the access site, the investigator will still be able to know the exact level of the access site, to properly hold pressure in the correct spot. (Fig.4A, Arrows). The *QuikClot® Radial®* pad is then applied over the access site, with the sheath still in place, with 1/3 of the pad being distal to the access site and 2/3 of the pad being proximal to the access site (Fig.4B, Arrows). The 3M™ Coban™ latex-free self-adherent wrap is then gently applied, wrapping 3-5 layers around the wrist to hold the *QuikClot® Radial®* pad in place (Fig. 4. C). When application is complete, the excess self-adherent wrap will be cut off (Fig. 4D). The 3 – 5 layers will then be hand massaged to allow the layers to adhere to each other (Fig. 4E). The sheath is then removed from the radial artery,

Fig 1. Application of the QuikClot® Radial® pad with the Coban™.

being pulled out from underneath the *QuikClot® Radial®* pad, with the investigator slightly pulling up on the distal portion of the pad, allowing for a small amount of bleeding to partially saturate the under surface of the *QuikClot® Radial®* pad to initiate the kaolin-blood reaction (Figs. 4, F and G). 5 minutes of firm manual compression is then held with several fingers on top of the *QuikClot® Radial®* pad, directly over the access site and just proximal to the access site, with the thumb wrapped under the wrist (Fig. 4H). After release of manual pressure, the investigator will observe for bleeding under the *QuikClot® Radial®* pad/Coban™ wrap for one minute (Fig. 4I). If there is not hemostasis, manual pressure will again be applied over the *QuikClot® Radial®* pad for another 5 minutes, and this cycle will be repeated until there is hemostasis. Once there is hemostasis, the previously applied Coban™ will be removed 25 minutes (\pm 5 minutes) after manual pressure is released, keeping the *QuikClot® Radial®* pad in place over the access site. A clear adhesive film dressing (Tegaderm™) is then applied over the *QuikClot® Radial®* pad, to be removed the following morning. If there is oozing/bleeding after the Tegaderm™ dressing is applied, the investigator may use his/her discretion to reapply manual pressure to the *QuikClot® Radial®* pad, or use mechanical compression with a TR Band®.

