1.3.2. The method for application of the TR Band®

After an end-procedure ACT is drawn and the blood pressure is recorded, application of the TR Band® for transradial hemostasis will be performed as described previously¹⁵ with the modifications described below. Briefly, the arterial access sheath is partially pulled out of the artery, exposing approximately 4 cm of sheath. A dry 4 inch by 4 inch gauze will be placed under the exposed sheath, cinched up to the skin entrance site of the sheath. The TR Band® will be applied snuggly around the wrist, with the sheath still in place, with the green dot of the TR Band® 2 – 3 mm proximal to the skin entrance site of the sheath. 10 mL of air will then be used to inflate the TR Band®. The sheath is then pulled out of the radial artery and out from under the TR Band®. The 4 x 4 gauze is then pulled out from under the TR Band®. If there is not hemostasis when the sheath is removed, additional air will be added in 1 – 2 mL increments until hemostasis occurs. When there is hemostasis, radial artery patency will be assessed by the reverse Barbeau test and recorded. Then, the TR Band® will remain in place for 60 minutes. At the end of 60 minutes (\pm 5 minutes) of compression, 2 mL of air will be removed, and then additional 2 mL at 80 minutes (\pm 5 minutes), and then 3 mL at 100 minutes (\pm 5 minutes), and then the remaining air slowly deflated over 30 seconds at 120 minutes (\pm 5 minutes). If oozing/bleeding occurs at any point during the weaning of air, the previously removed amount of air will be re-inflated into the TR Band®, and weaning will again commence in 20 minutes. Once all the air has been removed and hemostasis confirmed, the TR Band® will be removed, and a Band Aid or a dry gauze pad under a Tegaderm™ dressing will be placed over the skin entrance site, to be removed the following morning.

1.3.3 The method for application of the QuikClot® Radial® pad under a TR Band®

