After an end-procedure ACT is drawn and the blood pressure is recorded, the arterial access sheath will be partially pulled out of the radial artery, exposing approximately 4 cm of sheath. The level of the skin access site will be marked on the medial side of the palmar surface of the wrist with a sterile marker pen, so that once the pad is applied and covering the access site, the investigator will still be able to know the exact position of the skin access site, to properly apply pressure with the TR Band® in the correct spot. (Fig 5. A). The QuikClot® Radial® pad is then applied over the access site, with the sheath still in place, with approximately 1/2 of the pad being distal to the skin access site and 1/2 of the pad being proximal to the access site (Fig 5. C). This is best accomplished by placing the seam side of a QuikClot® Radial® pad face down on the sticky side of a Tegaderm™ (Fig 5. B), centering it in the middle of the Tegaderm™. The Tegaderm with a QuikClot® Radial® pad stuck to it is then positioned slightly

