7.3. Sample Size and Statistics

Based on the previous study¹⁷ on the use of TR Band® and our pilot study on the *QuikClot® Radial®* pad with either a Coban™ bandage or Tegaderm™ dressing for radial hemostasis, we anticipate an average initial successful hemostasis rate of 95% or higher in patients using the *QuikClot® Radial®* pad compression device, compared to an initial successful hemostasis rate of 84% in patients using the TR Band®, and no significant differences between the two *QuikClot® Radial®* pad arms. Using a type 1 error of 0.05 for each of the two comparisons of the *QuikClot® Radial®* pad with the TR Band® and power of 80% to detect an 11% difference in the rate of initial successful hemostasis between the TR Band® arm and either *QuikClot® Radial®* pad arm, a sample size of 100 will be needed for each of the three arms of the trial. Assuming that there may be a 50% screen failure rate (patients withdraw, ulnar access is used, radial access failure, events occur during the procedure that the investigator does not wish to enter the subject or the diagnostic only cases of the study are already filled), a total of up to 600 consecutive subjects undergoing transradial diagnostic cardiac catheterization and/or PCI, who sign informed consent to participate, will be recruited into the three arms of the trial.

An interim analysis was not originally planned for the study, but was conducted after enrolling 186 participants. The results obtained from the interim analysis showed that there was a failure to obtain initial hemostasis at 5 minutes in approximately 30% of the subjects in the QuikClot®/Tegaderm™ arm of the protocol, compared to a failure to obtain initial hemostasis of 11% in the TR Band® cohort (odds ratio = 3.2, 95% CI, 1.2 – 8.1, $p = 0.013$) and a failure to obtain initial hemostasis of 8% in the QuikClot®/Coban™ cohort (odds ratio = 4.7, 95% CI, 1.7 – 12.1, $p = 0.003$). Our DSMB committee reviewed the results and recommended to stop the Tegaderm™ only arm. We here institute a new arm 3 using a QuikClot® Radial® Pad under a TR Band® with 30 minutes of compression to replace the old arm 3 in this trial. The sample size of the new arm 3 is the same as the old arm 3, with 100 participants including 50 diagnostic-only cardiac catheterizations and 50 PCIs.

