Statistical summaries and analyses of data will be performed at Memorial Healthcare System. Descriptive analysis will be performed for all data including means and standard derivation or medians for continuous variables and proportions for categorical variables. The t-test will be used to describe the differences of clinical outcomes between the two compression devices after TRA, and a two-sided p-value of 0.05 will be considered to be statistically significant.

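### New Arm 3 v TR Band: no adjustment is planned for end-procedure ACT and blood pressure, although both are taken in every arm and most controls predate Arm 3

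*Combined protocol and SAP*

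**What the plan says.** The three application methods in the combined protocol and SAP begin with the same step.

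- Section 1.3.1 (Coban) and section 1.3.3 (pad under TR Band) both state: "After an end-procedure ACT is drawn and the blood pressure is recorded".
- Section 1.3.2 (TR Band alone): "After an end-procedure ACT is drawn and the blood pressure is recorded, application of the TR Band® for transradial hemostasis will be performed".

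Section 7.3 makes two commitments on analysis. One is descriptive: "Descriptive analysis will be performed for all data including means and standard derivation or medians for continuous variables". The other is inferential: "The t-test will be used to describe the differences of clinical outcomes between the two compression devices after TRA". No covariate, stratum or regression model is named, and neither ACT nor blood pressure is mentioned in that section.

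Section 3.1 states that 72 TR Band and 72 Coban patients were already enrolled when new Arm 3 was introduced, and that each arm is to reach 100, split 50 diagnostic-only and 50 PCI. Sections 3.1 and 4.4 place in new Arm 3 everyone whom REDCap assigns to the closed Tegaderm arm. They also place there patients assigned to Arms 1 or 2 once those arms, or their procedure-type quotas, are full.

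**The concern.** Both readings describe the patient just before the device is applied: how anticoagulated the patient is and what arterial pressure the site must hold. The device cannot change them. The documents treat anticoagulation as relevant. Section 1.1 links lack of it to radial artery occlusion. In section 1.4, the two cited femoral kaolin studies waited for ACT to fall to about 180 seconds before removing the sheath.

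In a fully randomized comparison, leaving such variables out costs only some precision. Arm 3 against TR Band is not fully randomized: most controls come from an earlier period, and many Arm 3 patients arrive by redirection. If ACT or pressure differs between periods, an unadjusted comparison of initial successful hemostasis, a primary endpoint, attributes the consequence to the device. Descriptive tables would show the imbalance without correcting for it.

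**Working it through.** **Inputs from the documents.** 100 per arm; 84% v 95% success; 80% power; alpha as in "Using a type 1 error of 0.05 for each of the two comparisons"; two-sided testing (section 7.3). Interim failure 11% TR Band and 8% Coban (section 7.3). Enrolment counts (section 3.1).

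**Assumptions, because the documents give no values.** Log-odds of failure of 0.5 or 0.8 per SD of the covariate, so odds multiplied by exp(0.5) = 1.65 or exp(0.8) = 2.2. A shift of 0.3 SD between arms. True device effect zero.

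**1. The plan's own figure.** With mean rate 0.895:

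n = [1.96 × √(2 × 0.895 × 0.105) + 0.842 × √(0.84 × 0.16 + 0.95 × 0.05)]² / 0.11² = 121 per arm.

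The stated 100 is not reproduced; two-sided power at 100 is 72.1%. That is a separate matter. Missing covariates do not cause it, and adjustment would need R² of about 15% to bring power at 100 per arm to 80% (79.9% on an unpooled-variance calculation).

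**2. Who is concurrent.** The counts agree: 217 + 156 = 373, and 28 + 28 + 100 = 156. TR Band patients who could be concurrent with Arm 3: 100 − 72 = 28. If the list is 1:1:1 (assumed), about 28 Arm 3 patients enter while Arms 1 and 2 fill. The other 72 or so have no concurrent control.

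**3. Size of a false effect in Arm 3 v TR Band.** To first order, bias ≈ shift × log-odds per SD × p(1 − p), with p = 0.11:

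- 0.3 × 0.5 × 0.11 × 0.89 = 0.015, or 1.5 points
- 0.3 × 0.8 × 0.11 × 0.89 = 0.023, or 2.3 points

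Simulation (100 per arm, 800 runs per setting) gave 1.4 and 2.4 points unadjusted, and −0.1 and 0.0 points for the adjusted standardised difference.

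A second simulation (4,000 runs, success 84% before any shift, unadjusted v adjusted linear risk difference with robust standard errors) used a wider range:

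| Odds ratio per SD | Shift (SD) | Unadjusted bias (points) | Type I error, unadjusted | Type I error, adjusted |
|---|---|---|---|---|
| 1.5 | 0.25 | 1.4 | 6.5% | 5.3% |
| 1.5 | 0.5 | 2.9 | 8.8% | 5.6% |
| 2 | 0.25 | 2.2 | 6.6% | 4.7% |
| 2 | 0.5 | 4.9 | 14.4% | 5.2% |
| 3 | 0.25 | 3.5 | 9.8% | 4.6% |
| 3 | 0.5 | 7.3 | 25.2% | 5.2% |

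Both simulations put all the drift into the covariate that the model contains, so they show the best that adjustment can do.

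**4. Precision in the randomized contrast.** With no shift, the standard error fell from 0.0443 to 0.0437 (1.4%) at 0.5 per SD, and from 0.0442 to 0.0434 (1.8%) at 0.8 per SD. Simulated power at 84% v 95% went from 75.1% to 74.7% (odds ratio 1.5), 75.0% to 75.9% (2) and 75.0% to 77.0% (3). Unadjusted type I error stayed at 5.2 to 5.4%, with bias about zero.

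**5. Events available.** At the interim rates, Coban v TR Band would have about 11 + 8 = 19 failures. With arm, procedure type, ACT and systolic pressure in the model, that is 19 / 4, or about 5 per coefficient.

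**The case against.** The strongest reply is that the drift is hypothetical. Nothing in the documents shows ACT or pressure changing over time. This is one center, section 1.6 sets the diagnostic heparin dose and an ACT target for heparin-treated PCI, and the procedure-type quota balances a main driver of ACT. Even under the assumed shift, 1.4 to 2.4 points is about 0.3 to 0.5 of the 4.4-point standard error, against an 11-point design difference. This limits the size of the point but does not remove it. The quota does not balance ACT within PCI, where section 1.6 leaves the choice of agent to the operator, and it does nothing for pressure.

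It is also fair that one end-procedure ACT with a common slope is a crude predictor. Failure can first appear at different times in the three arms, and infusions may continue after PCI.

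Five stronger readings are tempting, and the documents do not support them:

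- *The whole trial is confounded.* Coban v TR Band is randomized (section 4.4), and the test's error rate already covers chance imbalance.
- *Adjustment would noticeably raise power.* Step 4 shows about 0 to 2 points.
- *The bias rivals the observed effect.* The 3-point interim gap (11% v 8%) is TR Band v Coban, not the Arm 3 contrast.
- *The plan ignores these readings altogether.* Section 7.3 promises descriptive statistics for all data. What is missing is their use in inference.
- *Adjusting for ACT and pressure repairs Arm 3.* It cannot reach calendar time, operator learning or selection through redirected assignments.

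**Conclusion.** The point stands for new Arm 3 v TR Band on initial successful hemostasis. Randomization does not protect most of that comparison, two relevant readings are already taken before the device is applied, and the only inferential method named does not use them. The possible false effect is about 1.4 to 2.4 points under the assumptions of 11% failure, a 0.3 SD shift and failure odds multiplied by 1.65 to 2.2 per SD. It is larger only under stronger assumptions. No drift has been shown.

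For Coban v TR Band there is no bias to correct, and the gain in precision is negligible. Total time to hemostasis is largely fixed by the protocol durations in section 3.2.2 (30, 31 and 120 minutes before any recompression), so adjustment is not needed there. For radial artery occlusion it is optional and supportive. This is an inexpensive, partial safeguard that should accompany a concurrent-control analysis.

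**What to change.** In section 7.3, prespecify the following for initial successful hemostasis:

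1. A risk difference for each QuikClot arm against TR Band with 95% CI, standardised from a logistic model with arm, procedure type (diagnostic-only or PCI), end-procedure ACT and systolic pressure. Use penalised likelihood if failures are sparse, and show the unadjusted difference alongside.
2. ACT and blood pressure summarised by arm and by enrolment period (before and after the amendment).
3. A statement that, for Arm 3, this adjustment complements and does not replace an analysis restricted to concurrently randomized patients.

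Also confirm that ACT is drawn without knowledge of the assignment. Section 4.4 places randomization after the procedure and before sheath removal, but does not say whether it comes before or after the ACT draw.

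The cost is some SAP wording and a little more analysis, with a model that rests on few events. No new measurement is needed. The text should be settled before outcomes are compared between Arm 3 and TR Band.

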1.3.2. The method for application of the TR Band®

After an end-procedure ACT is drawn and the blood pressure is recorded, application of the TR Band® for transradial hemostasis will be performed as described previously¹⁵ with the modifications described below. Briefly, the arterial access sheath is partially pulled out of the artery, exposing approximately 4 cm of sheath. A dry 4 inch by 4 inch gauze will be placed under the exposed sheath, cinched up to the skin entrance site of the sheath. The TR Band® will be applied snuggly around the wrist, with the sheath still in place, with the green dot of the TR Band® 2 – 3 mm proximal to the skin entrance site of the sheath. 10 mL of air will then be used to inflate the TR Band®. The sheath is then pulled out of the radial artery and out from under the TR Band®. The 4 x 4 gauze is then pulled out from under the TR Band®. If there is not hemostasis when the sheath is removed, additional air will be added in 1 – 2 mL increments until hemostasis occurs. When there is hemostasis, radial artery patency will be assessed by the reverse Barbeau test and recorded. Then, the TR Band® will remain in place for 60 minutes. At the end of 60 minutes (\pm 5 minutes) of compression, 2 mL of air will be removed, and then additional 2 mL at 80 minutes (\pm 5 minutes), and then 3 mL at 100 minutes (\pm 5 minutes), and then the remaining air slowly deflated over 30 seconds at 120 minutes (\pm 5 minutes). If oozing/bleeding occurs at any point during the weaning of air, the previously removed amount of air will be re-inflated into the TR Band®, and weaning will again commence in 20 minutes. Once all the air has been removed and hemostasis confirmed, the TR Band® will be removed, and a Band Aid or a dry gauze pad under a Tegaderm™ dressing will be placed over the skin entrance site, to be removed the following morning.

1.3.3 The method for application of the QuikClot® Radial® pad under a TR Band®

After an end-procedure ACT is drawn and the blood pressure is recorded, the arterial access sheath will be partially pulled out of the radial artery, exposing approximately 4 cm of sheath. The level of the skin access site will be marked on the medial side of the palmar surface of the wrist with a sterile marker pen, so that once the pad is applied and covering the access site, the investigator will still be able to know the exact position of the skin access site, to properly apply pressure with the TR Band® in the correct spot. (Fig 5. A). The QuikClot® Radial® pad is then applied over the access site, with the sheath still in place, with approximately 1/2 of the pad being distal to the skin access site and 1/2 of the pad being proximal to the access site (Fig 5. C). This is best accomplished by placing the seam side of a QuikClot® Radial® pad face down on the sticky side of a Tegaderm™ (Fig 5. B), centering it in the middle of the Tegaderm™. The Tegaderm with a QuikClot® Radial® pad stuck to it is then positioned slightly

above the wrist (Fig 5. C), with the QuikClot® Radial® pad centered to the sheath, with one half of the pad above the skin access site and one half of the pad distal to the skin insertion site. The QuikClot® Radial® pad is then lowered onto the wrist, being held in the correct position with the Tegaderm dressing (Fig 5 D) A TR Band® will then be loosely applied over the QuikClot® pad covered with Tegaderm™, centering the TR Band® green dot 2 – 3 mm proximal to the marked skin entrance level (Fig 5, E). The sheath is then rapidly pulled, and the operator will observe for a small amount of blood on the undersurface of the QuikClot Radial Pad, then quickly fill the TR Band® with 8 – 10 mL of air (Fig 5. F, G, H). It is very important for blood to be in contact with the kaolin, to initial the hemostasis reaction. If no bleeding is seen on the under surface of the QuikClot® pad with the TR Band® still being uninflated, the operator may lift up the uninflated TR Band® and QuikClot® pad under it, to initiate a small amount of bleeding, and then fill the TR Band® with 8 – 10 mL of air. If there is continued bleeding after inflating the TR Band® with 8 – 10 mL of air, additional 1 – 2 mL increments of air should be added to obtain hemostasis. When there is hemostasis, radial artery patency will be assessed by the reverse Barbeau test and recorded. After 30 minutes of compression with the TR Band®, it will be deflated slowly over 1 minute. The deflated TR Band® will be left in place for 5 minutes, to allow for rapid reinflation if bleeding occurs. If there is hemostasis after 5 minutes of observation with the deflated TR Band®, the TR Band® will be removed, leaving the QuikClot® pad covered with the Tegaderm™ dressing. If bleeding occurs upon weaning of air, the TR Band® will be reinflated to obtain a total of 8 – 10 mL of air in the TR Band® bladder for an additional 20 minutes. The TR Band® will then again be slowly deflated over 1 minute, leaving the deflated TR Band® in place for an

Fig 5. Application of the QuikClot®Radial® pad under the TR Band®.

additional 5 minutes. This cycle will be repeated until there is hemostasis. The operator will have the option to remove the QuikClot® pad, and use just a TR Band®, if the subject has failed at least one subsequent re-inflation cycle.

